Attachment 5: 2-Week Follow Up

FOLLOW UP 2 WEEKS
PHYSICIAN ASSESSMENT

OVER THE LAST WEEK, HOW TROUBLESOME HAVE THE FOLLOWING SYMPTOMS BEEN? PLEASE PLACE A MARK ON THE LINE.	
	Not troublesome Worst thinkable/troublesome
Nasal blockage/obstruction/congestion	
Nasal discharge/drainage out of the front or back of nose	
Pain/pressure in nose or sinuses	
Sense of smell	
OVERALL ASSESSMENT OF NASAL AND SINUS PROBLEMS	

Change in nasal symptoms and use of device

Please rate changes in your nasal symptoms and use of device.

Symptom	None	Mild	Moderate	High
Improvement in nasal obstruction/stuffiness	0	1	2	3
Improvement in nasal drainage/discharge	0	1	2	3
Improvement in nasal or sinus pressure	0	1	2	3
Improvement in ability to smell	0	1	2	3
Use of the Device				
Pain with use of device	None	Mild	Moderate	Severe
Comfort and ease of use	Poor	Low	Moderate	High
Bleeding:	Yes	No		
Willingness to use again	Yes	No		
Willingness to recommend to friend/family	Yes	No		

Total Nasal Symptom Score

Please answer all questions to the best of your ability. This information will assist us in understanding and treating symptoms. Please rate how your symptoms have been over the **past week**.

Symptom	None	Mild: Symptom clearly present but easily tolerated	Moderate: Symptom bothersome but tolerable	Severe: Symptom difficult to tolerate – interferes with activities
Nasal congestion/obstruction	0	1	2	3
Runny nose/secretions	0	1	2	3
Nasal itching	0	1	2	3
Sneezing	0	1	2	3
Sleep difficulty with nasal symptoms	0	1	2	3

NOSE Scale

Please help us to better understand the impact of nasal obstruction on your quality of life by completing the following survey. Thank you!

Over the past **ONE month**, how much of a problem were the following conditions for you?

	Not a problem	Very mild problem	Moderate problem	Fairly bad problem	Severe problem
Nasal congestion or stuffiness	0	1	2	3	4
Nasal blockage or obstruction	0	1	2	3	4
Trouble breathing through my nose	0	1	2	3	4
Trouble sleeping	0	1	2	3	4
Unable to get enough air through my nose during exercise or exertion	0	1	2	3	4

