10.0 Data Management

All analyses and graphs will be performed with SPSS 24.0, Sample Power 3.0, and Sigma Plot 10.0 (SPSS, Chicago, IL.). Disease information and demographic variables, such as age, gender, race, quality of life (QOL) scores, and VAS scores will be summarized using frequencies, means, and standard deviation as appropriate. Outcome metrics will be compared between baseline and 5 minutes (AIM 1), baseline and 2 weeks (AIM 2), and baseline and 4-6 weeks (AIM 3). Categorical variables will be compared using Chi Square or McNemar's test. Continuous variables will be compared using One-Way ANOVA with repeated measures followed by post-hoc analysis. Data regarding safety and patient satisfaction will be summarized for each time point. A p-value ≤ 0.05 will be considered statistically significant. Due to the exploratory nature of this study, no p-value correction (ie Bonferroni) will be applied. If appropriate, subgroup analysis can be performed based on underlying disease classification (allergic rhinitis, nonallergic rhinitis, CRSsNP, CRSwNP).

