Attachment 2: Baseline Questionnaires**BASELINE QUESTIONNAIRES**

PATIENT QUESTIONS													
How long have you had nasal problems?	<3 months 3-6 months 6-12 months 1-3 years >3 years												
OVER THE LAST WEEK, HOW TROUBLESONE HAVE THE FOLLOWING SYMPTOMS BEEN? PLEASE PLACE A MARK ON THE LINE.													
	
  
 Not troublesome	Worst thinkable/troublesome	
   
 ◆————◆	◆————◆	
  
	Not troublesome	Worst thinkable/troublesome	◆————◆	◆————◆	◆————◆	◆————◆	◆————◆	◆————◆	◆————◆	◆————◆	◆————◆	◆————◆
Not troublesome	Worst thinkable/troublesome												
◆————◆	◆————◆												
◆————◆	◆————◆												
◆————◆	◆————◆												
◆————◆	◆————◆												
◆————◆	◆————◆												
Nasal blockage/obstruction/congestion	◆————◆												
Nasal discharge/drainage out of the front or back of nose	◆————◆												
Pain/pressure in nose or sinuses	◆————◆												
Sense of smell	◆————◆												
OVERALL ASSESSMENT OF NASAL AND SINUS PROBLEMS	◆————◆												

BASELINE Total Nasal Symptom Score

Please answer all questions to the best of your ability. This information will assist us in understanding and treating symptoms. Please rate how your symptoms have been over the **past week**.

Symptom	None	Mild: Symptom clearly present but easily tolerated	Moderate: Symptom bothersome but tolerable	Severe: Symptom difficult to tolerate – interferes with activities
Nasal congestion/obstruction	0	1	2	3
Runny nose/secretions	0	1	2	3
Nasal itching	0	1	2	3
Sneezing	0	1	2	3
Sleep difficulty with nasal symptoms	0	1	2	3

BASELINE NOSE scale

Please help us to better understand the impact of nasal obstruction on your quality of life by completing the following survey. Thank you!

Over the past **ONE month**, how much of a problem were the following conditions for you?

	Not a problem	Very mild problem	Moderate problem	Fairly bad problem	Severe problem
Nasal congestion or stuffiness	0	1	2	3	4
Nasal blockage or obstruction	0	1	2	3	4
Trouble breathing through my nose	0	1	2	3	4
Trouble sleeping	0	1	2	3	4
Unable to get enough air through my nose during exercise or exertion	0	1	2	3	4

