Attachment 3: Baseline SNOT-22

BASELINE SNOT22

Problem as bad as it can be	Severe Problem	Moderate Problem	Mild or slight problem	Very mild problem	No problem	
0	1	2	3	4	5	1. Considering how severe the problem is when you experience it and how frequently it happens, please rate each item below on how "bad" it is over the last 2 weeks by circling the number that corresponds with how you feel using this scale: →
0	1	2	3	4	5	1. Need to blow nose
0	1	2	3	4	5	2. Sneezing
0	1	2	3	4	5	3. Runny nose
0	1	2	3	4	5	4. Cough
0	1	2	3	4	5	5. Post-nasal discharge
0	1	2	3	4	5	6. Thick nasal discharge
0	1	2	3	4	5	7. Ear fullness
0	1	2	3	4	5	8. Dizziness
0	1	2	3	4	5	9. Ear pain
0	1	2	3	4	5	10. Facial pain/pressure
0	1	2	3	4	5	11. Difficulty falling asleep
0	1	2	3	4	5	12. Wake up at night
0	1	2	3	4	5	13. Lack of a good night's sleep
0	1	2	3	4	5	14. Wake up tired
0	1	2	3	4	5	15. Fatigue
0	1	2	3	4	5	16. Reduced productivity
0	1	2	3	4	5	17. Reduced concentration
0	1	2	3	4	5	18. Frustrated/restless/irritable
0	1	2	3	4	5	19. Sad

20. Embarrassed	0	1	2	3	4	5
21. Loss of smell or taste	0	1	2	3	4	5
22. Nasal obstruction	0	1	2	3	4	5

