Attachment 6: SNOT-22 Survey**SNOT22 Survey**

	No problem	Problem as bad as it can be				
		Severe Problem	Moderate Problem	Mild or slight problem	Very mild problem	→
2. Considering how severe the problem is when you experience it and how frequently it happens, please rate each item below on how "bad" it is by circling the number that corresponds with how you feel using this scale: →						
1. Need to blow nose	0	1	2	3	4	5
2. Sneezing	0	1	2	3	4	5
3. Runny nose	0	1	2	3	4	5
4. Cough	0	1	2	3	4	5
5. Post-nasal discharge	0	1	2	3	4	5
6. Thick nasal discharge	0	1	2	3	4	5
7. Ear fullness	0	1	2	3	4	5
8. Dizziness	0	1	2	3	4	5
9. Ear pain	0	1	2	3	4	5
10. Facial pain/pressure	0	1	2	3	4	5
11. Difficulty falling asleep	0	1	2	3	4	5
12. Wake up at night	0	1	2	3	4	5
13. Lack of a good night's sleep	0	1	2	3	4	5
14. Wake up tired	0	1	2	3	4	5
15. Fatigue	0	1	2	3	4	5
16. Reduced productivity	0	1	2	3	4	5
17. Reduced concentration	0	1	2	3	4	5
18. Frustrated/restless/irritable	0	1	2	3	4	5
19. Sad	0	1	2	3	4	5

20. Embarrassed	0	1	2	3	4	5
21. Loss of smell or taste	0	1	2	3	4	5
22. Nasal obstruction	0	1	2	3	4	5

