Attachment 7: 5-Week Follow Up**FOLLOW UP 5 WEEKS**

OVER THE LAST WEEK, HOW TROUBLESOME HAVE THE FOLLOWING SYMPTOMS BEEN? PLEASE PLACE A MARK ON THE LINE.		
	Not troublesome	Worst thinkable/troublesome
Nasal blockage/obstruction/congestion	◆————◆	◆————◆
Nasal discharge/drainage out of the front or back of nose	◆————◆	◆————◆
Pain/pressure in nose or sinuses	◆————◆	◆————◆
Sense of smell	◆————◆	◆————◆
OVERALL ASSESSMENT OF NASAL AND SINUS PROBLEMS	◆————◆	◆————◆

Change in nasal symptoms and use of device

Please rate changes in your nasal symptoms and use of device.

Symptom	None	Mild	Moderate	High
Improvement in nasal obstruction/stuffiness	0	1	2	3
Improvement in nasal drainage/discharge	0	1	2	3
Improvement in nasal or sinus pressure	0	1	2	3
Improvement in ability to smell	0	1	2	3
Use of the Device				
Pain with use of device	None	Mild	Moderate	Severe
Comfort and ease of use	Poor	Low	Moderate	High
Bleeding:	Yes	No		
Willingness to use again	Yes	No		
Willingness to recommend to friend/family	Yes	No		

Total Nasal Symptom Score

Please answer all questions to the best of your ability. This information will assist us in understanding and treating symptoms. Please rate how your symptoms have been over the **past week**.

Symptom	None	Mild: Symptom clearly present but easily tolerated	Moderate: Symptom bothersome but tolerable	Severe: Symptom difficult to tolerate – interferes with activities
Nasal congestion/obstruction	0	1	2	3
Runny nose/secretions	0	1	2	3
Nasal itching	0	1	2	3
Sneezing	0	1	2	3
Sleep difficulty with nasal symptoms	0	1	2	3

NOSE Scale

Please help us to better understand the impact of nasal obstruction on your quality of life by completing the following survey. Thank you!

Over the past **ONE month**, how much of a problem were the following conditions for you?

	Not a problem	Very mild problem		Moderate problem	Fairly bad problem	Severe problem
Nasal congestion or stuffiness	0	1		2	3	4
Nasal blockage or obstruction	0	1		2	3	4
Trouble breathing through my nose	0	1		2	3	4
Trouble sleeping	0	1		2	3	4
Unable to get enough air through my nose during exercise or exertion	0	1		2	3	4

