Attachment 8: SNOT-22 Survey**SNOT22 Survey**

	No problem	Problem as bad as it can be				
		Severe Problem	Moderate Problem	Mild or slight problem	Very mild problem	
3. Considering how severe the problem is when you experience it and how frequently it happens, please rate each item below on how "bad" it is by circling the number that corresponds with how you feel using this scale: →						
1. Need to blow nose	0	1	2	3	4	5
2. Sneezing	0	1	2	3	4	5
3. Runny nose	0	1	2	3	4	5
4. Cough	0	1	2	3	4	5
5. Post-nasal discharge	0	1	2	3	4	5
6. Thick nasal discharge	0	1	2	3	4	5
7. Ear fullness	0	1	2	3	4	5
8. Dizziness	0	1	2	3	4	5
9. Ear pain	0	1	2	3	4	5
10. Facial pain/pressure	0	1	2	3	4	5
11. Difficulty falling asleep	0	1	2	3	4	5
12. Wake up at night	0	1	2	3	4	5
13. Lack of a good night's sleep	0	1	2	3	4	5
14. Wake up tired	0	1	2	3	4	5
15. Fatigue	0	1	2	3	4	5
16. Reduced productivity	0	1	2	3	4	5
17. Reduced concentration	0	1	2	3	4	5
18. Frustrated/restless/irritable	0	1	2	3	4	5
19. Sad	0	1	2	3	4	5

20. Embarrassed	0	1	2	3	4	5
21. Loss of smell or taste	0	1	2	3	4	5
22. Nasal obstruction	0	1	2	3	4	5

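### At both follow-ups, one-directional improvement items and willingness items precede TNSS and NOSE, with no counterpart at baseline, so any same-visit order effect would enter the uncontrolled Aim 2 and Aim 3 changes in full (minor)

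*Combined protocol and SAP*

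**What the plan says.** Baseline assessment uses Attachment 2, which has VAS lines, then "BASELINE Total Nasal Symptom Score", then NOSE, followed by "Attachment 3: Baseline SNOT-22". Neither contains questions about change or about the device.

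The 2-week form (Attachment 5) starts with the same VAS lines and then inserts a block with the instruction "Please rate changes in your nasal symptoms and use of device". Its four symptom items are worded like "Improvement in nasal obstruction/stuffiness" and are answered from None to High. Items on pain, comfort and bleeding follow, then two on willingness, the last being "Willingness to recommend to friend/family". TNSS and NOSE come next on the same form. SNOT-22 is a separate sheet, "Attachment 6: SNOT-22 Survey". The 5-week form (Attachment 7) repeats this layout, with its SNOT-22 in "Attachment 8: SNOT-22 Survey".

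Section 10.0 plans comparisons between "baseline and 2 weeks (AIM 2), and baseline and 4-6 weeks (AIM 3"). It sets significance at p ≤ 0.05 without multiplicity correction and calls the study exploratory. Section 3.0 has all subjects using the device, and no comparator is described. Section 6.0 has the 4-6 week surveys sent by email. No section sets an order of administration or discusses order effects.

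**The concern.** A subject who has just graded their own improvement, and said whether they would recommend the device, next meets scales that ask about the same symptoms. The first TNSS item, the first two NOSE items and SNOT-22 item 22 all concern congestion or obstruction, which the first improvement item has just covered. People tend to answer consistently with what they have just said, and the improvement items offer no way to report worsening. If there is a tilt, it is plausibly towards lower follow-up scores.

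The questionnaire context therefore differs between the two time points being compared. With no control arm completing the same forms, nothing in the design subtracts such an effect. Three scales at two follow-ups are exposed, which makes 3 × 2 = 6 baseline comparisons.

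**Working it through.** **Step 1. Order of instruments, from Attachments 2 to 8.**

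| Assessment | Printed order |
|---|---|
| Baseline (Att. 2, 3) | VAS, TNSS, NOSE; then SNOT-22 |
| 5 minutes (Att. 4) | VAS, improvement items, pain, comfort, bleeding; no TNSS, NOSE or SNOT-22 |
| 2 weeks (Att. 5, 6) | VAS, improvement items, pain, comfort, bleeding, willingness items, TNSS, NOSE; then SNOT-22 |
| 5 weeks (Att. 7, 8) | as at 2 weeks |

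TNSS and NOSE follow the block on the same form at both follow-ups. SNOT-22 follows it only if the sheets are used in attachment order.

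**Step 2. Where an order effect would go.** Let b be the mean shift caused by the lead-in, in SDs of the change score. The baseline shift is zero because there is no lead-in, and no control arm is subtracted. Hence

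expected observed change = true change + b.

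**Step 3. Scale, for illustration only.** The plan gives 40 subjects (section 5.0) and a significance level of 0.05 (section 10.0). It gives no SD, effect size or power figure, so there is nothing of the plan's own to reproduce. These inputs are assumptions:
- the values of b;
- a two-sided test (sidedness is not stated);
- a paired t-test standing in for one post-hoc contrast of the planned repeated-measures ANOVA;
- no true change;
- a 20% loss giving 40 × 0.8 = 32 pairs.

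The rejection probability is P(|T| > t(0.975, n−1)), where T is noncentral t with n−1 degrees of freedom and noncentrality b√n. For n = 40, √40 = 6.325, so b = 0.1, 0.2 and 0.3 give noncentralities of 0.63, 1.26 and 1.90.

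| Assumed b | n = 40 | n = 32 |
|---|---|---|
| 0 | 5.0% | 5.0% |
| 0.1 SD | 9.5% | 8.5% |
| 0.2 SD | 23.5% | 19.5% |
| 0.3 SD | 45.7% | 37.6% |

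An observed mean change of t(0.975, n−1)/√n SD reaches p = 0.05 on its own. That is 2.023/6.325 = 0.32 SD for n = 40 and 2.040/5.657 = 0.36 SD for n = 32.

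**Step 4. What re-ordering removes.** With the improvement and willingness items placed last, their same-visit contribution to b is zero. Two things remain. Subjects will have met the improvement items at 5 minutes, and the improvement and willingness items at 2 weeks, before later ratings. The pain, comfort and bleeding items, if left in place, still precede TNSS at follow-up only.

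**The case against.** The strongest reply is that no harm has been shown. Nothing in the documents establishes that priming occurs. Each improvement item offers None, and the same block asks about pain, poor comfort and bleeding, so a consistency effect could push a non-responder towards reporting no change. This stands as to existence and size. The direction is only plausible, and it rests on the one-sided wording of the improvement items.

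Second, the order of use is inferred. The Schedule of Events (section 9.1) lists the instruments in another sequence, though it need not be an administration order. Section 9.0 says clinicians ask some of the questions, and the 2-week form carries a physician-assessment heading. This stands for SNOT-22. For TNSS and NOSE, the printed order on a single form is the best evidence available.

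Third, the figures in the table would follow from any bias of that size. This also stands. A reader might infer that up to 45.7% of null trials would come out positive because of form order, but the documents give no basis for any value of b. Nor would moving the items restore a 5% error rate for a device effect. Enrolment on a congestion VAS above 5 (section 4.0) and the lack of a control leave regression to the mean and placebo response in the same change scores.

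Fourth, a reader might infer that the VAS is untouched because it precedes the block. It escapes only same-visit priming. The improvement items have already been met at 5 minutes, and the whole block at 2 weeks before the last VAS.

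Finally, sending the whole block to the end would place the forms' structured pain and bleeding questions behind 5 + 5 + 22 = 32 further items. In an emailed survey, a partly completed response could lose them. This is a good reason for a narrower change.

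**Conclusion.** The point holds in a limited form. The layout asymmetry is a matter of record for TNSS and NOSE at both follow-ups, and for SNOT-22 if attachment order is followed. Because Aims 2 and 3 are uncontrolled comparisons with baseline, any same-visit order effect would enter the change in full. The documents support neither the claim that these scales are in fact biased nor any estimate of the amount.

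Severity is minor. The primary aim is outside this point, since the 5-minute form has none of the three scales. The exposed comparisons belong to secondary aims of a 40-subject exploratory pilot, and the missing control group is a much larger limitation of the same change scores. The point is worth acting on because the asymmetry is avoidable at almost no cost.

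**What to change.** In Attachments 5 and 7, move the four improvement items and the two willingness items to the end of the packet, after TNSS, NOSE and SNOT-22. Leave the pain, comfort and bleeding items where they are, so that a partly completed survey does not lose safety data. State in the protocol one fixed order for the scales (VAS, TNSS, NOSE, SNOT-22) at baseline, 2 weeks and 4-6 weeks, and apply it to the emailed packet with the moved items on the last page.

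The cost is re-ordering two forms and adding one sentence, with no new items, visits, staff or subjects. The downside is that the improvement and willingness answers come last and may be missing more often. Carry-over from earlier visits is not removed and should be acknowledged when the results are interpreted.

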1.0 Objectives / Specific Aims

- Primary: To determine the safety and efficacy of a single SinuSonic intervention.
- Secondary: Secondary objectives of this study is to determine:
 - the safety and efficacy of a twice daily SinuSonic intervention over 2 weeks.
 - the safety and efficacy of a twice daily SinuSonic intervention over 4 to 6 weeks.

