3.0 Intervention to be studied

- Initial intervention: Subjects will use the SinuSonic device for 3 minutes in the clinic setting.
- Secondary intervention: Subjects will use SinuSonic device twice daily for 3 minutes in the home setting for 14 days.
- Tertiary intervention: Subjects will continue to use the SinuSonic device twice daily for 3 minutes in the home setting for 2-4 weeks.

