4.0 Inclusion and Exclusion Criteria/ Study Population

The study population will consist of individuals present for care at the Otolaryngology clinics at the Medical University of South Carolina with nasal congestion, friends/family members of patients presenting for care at MUSC’s Otolaryngology clinics.

Inclusion Criteria

- Adults \geq 18 years of age
- Complaints of nasal congestion present for 2 weeks or more and a qualifying nasal congestion score of >5 (10 point VAS scale).

Exclusion Criteria

- Fixed structural cause of nasal congestion (moderate or severe septal deviation, moderate or severe nasal valve collapse, Grade 3-4 polyp)
- Inability to read and understand English
- Allergic sensitivity to silicone or any other component of device
- History of severe nose bleeding within last 3 months
- Anticoagulation (Aspirin ok)
- Known pregnancy
- Current nasal crusting or ulceration revealed on rhinoscopy
- Inability to perform treatment due to underlying medical condition

- Topical decongestant use in last week

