9.1 Schedule of Events

Phase	Screening	Treatment		
		0	2	4-6
Week	0	0	2	4-6
Visit	1	2	3	4
Informed Consent	x			
Inclusion/Exclusion Criteria	x			
Medical History	x			
Height	x			
Rhinoscopy	x		x	
Vital Signs	x			
Pregnancy Test	x			
Distribution of SinuSonic	x			
NOSE Questionnaire	x		x	x
SNOT-22	x		x	x
TNSS Questionnaire	x		x	x
Global Assessment of Nasal/Sinus Problems	x	x	x	x
PNIF	x	x	x	

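### Both follow-up SNOT-22 forms omit the baseline's two-week window, and the one-month window of the week-2 NOSE reaches back before treatment (50%–55% of rated days at a day-14 visit)

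*Combined protocol and SAP*

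**What the plan says.** A secondary objective (section 1.0) is to determine "the safety and efficacy of a twice daily SinuSonic intervention over 2 weeks". Section 3.0 sets the exposure behind it: "Subjects will use SinuSonic device twice daily for 3 minutes in the home setting for 14 days". Section 9.1 schedules NOSE and SNOT-22 at screening, week 2 and weeks 4–6, and gives no window in days for the week-2 visit. Section 10.0 compares baseline with 2 weeks under Aim 2 and baseline with 4–6 weeks under Aim 3. It adds: "Continuous variables will be compared using One-Way ANOVA with repeated measures followed by post-hoc analysis". The pairs to be tested post hoc are not named.

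The forms set these recall periods:

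- **NOSE:** one month on all three forms (Attachments 2, 5 and 7). The week-2 form reads "Over the past ONE month, how much of a problem were the following conditions for you".
- **SNOT-22:** the last two weeks at baseline (Attachment 3). The follow-up forms (Attachments 6 and 8) carry the same instruction without any period.
- **VAS and TNSS:** the past week at baseline, week 2 and the last follow-up (Attachments 2, 5 and 7).

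Nothing in the protocol comments on these differences.

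**The concern.** A change score is easiest to read when both ratings cover periods of the same length and the later period lies within treatment. Each questionnaire misses one of these conditions.

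For SNOT-22, the period is fixed at baseline and left open afterwards. One subject may answer for today and another for the last month. Later analysis cannot recover which period a subject had in mind, so the gap can be closed only on the form.

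For NOSE, the length is constant, but at week 2 the month is longer than the time on treatment. The week-2 rating therefore takes in days before first use that the baseline form has already rated. Two readings are at stake. The week-2 change may look smaller than the change reached on treatment. The later score may then look like a further gain, although nothing has changed except that the month has filled with treated days. No control group is described that would show this.

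**Working it through.** The protocol gives no figure on this point, so there is nothing to reproduce. The inputs are 14 days of home use (section 3.0), a one-month NOSE window (Attachments 2, 5 and 7) and follow-up at 2 and 4–6 weeks (section 9.1). The assumptions are a month of M = 28, 30 or 31 days, baseline rating and first use on day 0, and a constant effect from day 0.

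**Step 1. Share of the week-2 NOSE month before treatment, (M − v)/M, for a visit on day v = 14.**

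- M = 28: 14/28 = 50.0%
- M = 30: 16/30 = 53.3%
- M = 31: 17/31 = 54.8%

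These 14 to 17 days also lie inside the baseline month. If the clinic use on day 0 counts as a treated day, the range is 13/28 = 46.4% to 16/31 = 51.6%. Because no visit window is stated, an assumed visit on days 11 to 17 gives 11/28 = 39.3% (day 17, M = 28) to 20/31 = 64.5% (day 11, M = 31).

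**Step 2. Share of a constant effect retained at week 2, with all days weighted equally, v/M.** Day 14: 14/28 = 0.500, 14/30 = 0.467, 14/31 = 0.452.

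**Step 3. The same share if recent days weigh more.** With weight 0.5^(days ago/h), the share is (1 − 0.5^(v/h)) / (1 − 0.5^(M/h)). For v = 14 and M = 30:

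- h = 14 days: 0.500/0.774 = 0.646
- h = 7 days: 0.750/0.949 = 0.791
- h = 3 days: 0.961/0.999 = 0.962

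Across M = 28 to 31 the range is 0.637 to 0.962. The half-lives are assumptions, and the protocol says nothing on how patients weigh days.

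**Step 4. The last assessment, equal weights.** On day 28 the on-treatment share is 28/28 = 1.000, 28/30 = 0.933 or 28/31 = 0.903. On days 35 and 42 it is 1.000.

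**Step 5. Apparent further gain from day 14 to weeks 4–6 when the true effect is constant.** With equal weights it runs from 0.903 − 0.452 = 0.451 (0.452 before rounding, 14/31) to 1.000 − 0.452 = 0.548, so 45%–55% of the effect. With the recency weights it runs from 0.038 to 1.000 − 0.637 = 0.363, so 4%–36%.

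**Step 6. SNOT-22.** No share can be computed for the follow-up forms, because they state no period. If the baseline's two weeks were printed, a day-14 visit would be 14/14 = 100% on treatment, a day-11 visit 11/14 = 79%, and weeks 4–6 100%. The length of the baseline window therefore suits the follow-up. The fault is only that it is missing.

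**The case against.** The strongest reply is that little harm is shown. Aim 2 is secondary, and section 10.0 says "Due to the exploratory nature of this study, no p-value correction (ie Bonferroni) will be applied". The same NOSE month at all three visits keeps the instrument constant. Dilution moves a change toward zero and does not create one. Patients may weigh recent days heavily, and with a three-day half-life almost all the effect is retained. On SNOT-22, the follow-up instruction still asks about frequency, which implies a period, and the same subjects saw two weeks at baseline. No aim names a comparison of week 2 with weeks 4–6. All of this stands, and it keeps the point minor. It does not remove either gap: the SNOT-22 period is still unstated, and the unnamed post-hoc pairs leave room for the misreading in step 5.

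A reader might infer more than the documents support:

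- **That week-2 NOSE should not be tested.** Dilution alone is no reason to withdraw a planned comparison. Section 6.0 places screening and week 2 in clinic but sends the 4–6 week surveys by email, so withdrawal would leave NOSE inference resting on a changed mode of collection.
- **That the week-2 NOSE result is biased toward no effect overall.** Entry requires a congestion VAS above 5 and no control group is described, so regression to the mean can push the change the other way.
- **That power is lost.** This depends on the assumed recall weights and on how averaging over days alters the variance, and the protocol gives neither.
- **That the SNOT-22 ratings do cover different periods.** They may, but the forms do not show it.
- **That the primary aim is affected.** Neither questionnaire is scheduled at the 5-minute assessment (section 9.1, Attachment 4). The 5-minute VAS does ask about symptoms after use where baseline asks about the last week, but that is a separate question.

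**Conclusion.** The point holds as a minor one, confined to the secondary aims. The SNOT-22 omission is a plain fact of the forms. Its effect on Aims 2 and 3 cannot be sized or given a direction. The NOSE overlap is also plain: 50%–55% of rated days for a day-14 visit and a 28–31 day month, and 39%–65% if the visit falls on days 11 to 17. How much it matters rests on an assumed constant effect and on recall weights the documents cannot supply. The dilution ranges from severe (45% retained) to slight (96% retained), and the net bias is not determined. The one inference to rule out in advance is reading a NOSE difference between week 2 and weeks 4–6 as benefit from longer use, since the window alone could produce it.

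**What to change.** 1. Print the baseline phrase, *over the last 2 weeks*, on both follow-up SNOT-22 forms (Attachments 6 and 8), before they are completed.

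2. Leave the NOSE wording and the planned baseline to 2-week NOSE comparison as they are, and add to section 10.0:

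   *Because NOSE asks about one month, the week-2 result is reported with the share of that month before first use, calculated from actual visit dates, and is read as a likely diluted estimate. A difference in NOSE between 2 weeks and 4–6 weeks is not used to claim added benefit from longer use; the VAS and TNSS (one-week windows) are used to describe change between those visits.*

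Using actual dates avoids building in a day-14 visit that the schedule does not guarantee.

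The cost is one phrase on two forms, two sentences in section 10.0, and one NOSE contrast that is not used for claims. All planned data are still collected and all comparisons named in the aims remain.
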